Figure 1. Overall Study Design for Cohorts 1, 1a, 2, and 3

Cohort	Age (years)	Corresponding Adult Dose
1	11 to 17	50 mg QD
1a*	11 to 17	To be determined based on DMC recommendation
2	11 to 17	200 mg QD
3	2 to 10	50 mg QD, 100 mg QD, OR 200 mg QD

*Cohort 1a is an optional interim dose cohort that may be enrolled only if needed per DMC recommendation and Sponsor decision, in the event of a safety concern in sentinel participants in Cohort 1.

[figure not shown]
[figure not shown]

Figure 2. Overall Study Design for Cohorts 4, 5, 6, 8, 7, and 9

Note: Any participant enrolled under protocol amendment 3 may be re-consented to protocol amendment 4 and receive the 12-week treatment course; however, because they will have already contributed PK data, they will not be required to have blood draws for tildacerfont concentration on Days 1 and 14 between 0.5 to- 1.5 hours and between 3 to 5 hours post dosing. Additionally, any participant enrolled under amendment 4 (or any other tildacerfont study) may be re-consented and enrolled under protocol amendment 5.

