### 9.2.2 *Re-Enrolled, Different Cohort*

Re-enrolled subjects will have more than one set of cohort data. Therefore, the summary results by cohort will be summarizing these subjects by unique enrollment experience (per cohort) rather than per subject for summaries of disposition, protocol deviations and study drug exposure. Subjects who re-enrolled into two or more different cohorts will have multiple baseline values for safety and efficacy summaries – a set of baseline values for their first cohort experience, and a set of baseline values for each subsequent cohort experience.

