#### 13.1.1.1 Reporting Results

##### 13.1.1.1.1 Descriptive Statistics

Frequency and proportion (expressed as percentages) of responders will be calculated along with 95% Exact (Clopper-Pearson) CIs and reported for the study and each cohort.

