## **13.2 Exploratory Efficacy Analysis**

### *13.2.1 Change from Baseline in PD Biomarkers*

The PD analysis set will be used for exploratory efficacy analyses.

Descriptive statistics (11-point) for the exploratory biomarker assessments, change from baseline, percent change from baseline, and geometric mean ratio will be presented by cohort, scheduled time points including Baseline, and by subgroup ([Section 10.7](#)). PD biomarkers include ACTH, 17-OHP, A4, and testosterone.

The back-transformed log scale change from baseline and 95% confidence intervals will be calculated for each post-baseline visit by cohort and overall using a balanced bootstrap method. The bootstrapping will consist of 1,000 replicate samples using a uniform random number generation by the method of Fishman and Moore with a SEED = 42, where the sampling unit is the subject ID which uniquely identifies each enrollment experience for a given subject.

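### The overall bootstrap confidence intervals for hormone change resample enrollments rather than people, so they are too narrow if re-enrolled participants respond alike each time

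*SAP*

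**What the plan says.** The interval is specified in SAP 13.2.1: "The back-transformed log scale change from baseline and 95% confidence intervals" are "calculated for each post-baseline visit by cohort and overall using a balanced bootstrap method". There are 1,000 replicates, and "the sampling unit is the subject ID which uniquely identifies each enrollment experience for a given subject".

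Repeat enrollment is foreseen in both documents. The note to Figure 2 in Protocol 3.1 says that "any participant enrolled under amendment 4 (or any other tildacerfont study) may be re-consented and enrolled under protocol amendment 5". Exclusion criterion 9 (Protocol 4.1.2) admits people with earlier tildacerfont exposure after at least two weeks off drug. SAP 9.2.2 states that "Re-enrolled subjects will have more than one set of cohort data" and gives each such person "a set of baseline values for their first cohort experience, and a set of baseline values for each subsequent cohort experience". Each enrollment therefore produces its own change score.

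SAP 13 drops data collected under Protocol v3.0 from the efficacy analyses. People who enrolled under v4.0 and again under v5.0 stay in with both records. The text consulted has no person-level clustering, no rule of one record per person for the pooled hormone estimate, and no sensitivity analysis for repeats.

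**The concern.** A bootstrap reproduces sampling variability only if the units it draws are independent. A child treated in Cohort 2 and later in Cohort 6 supplies two change scores that share that child's drug clearance and disease. If these move together, the two scores carry less information than scores from two different children. Drawing them separately credits the pooled estimate with information it does not have.

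The study has no hypothesis tests, so type I error is not at issue. What is at stake is the stated precision. Intervals are the plan's main statement of uncertainty, and SAP 4 says its analyses may be used in regulatory submissions and manuscripts.

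**Working it through.** The plan states no interval width, standard deviation, number of repeats or within-person correlation, so there is no figure of its own to reproduce. The check asks how far the SAP interval departs from a correct one under stated assumptions.

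**Inputs**
- Number of pooled records: N = 70, the cap in SAP 7. The cohort sizes in SAP Table 1 add up to it: 5+5+5+10+5+10+5+5+10+10 = 70. Treating the cap as a count of enrollments is an assumption.
- Number of people who contribute two records: m = 5, 10, 20 or 25 (assumed). Planned enrollment in Cohorts 1–3, with Cohort 1a, is 25, so m = 25 is an upper-range case.
- Correlation between one person's two log changes: ρ = 0.3 to 0.5 (assumed).

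**Formula.** With a common variance σ², each pair adds 2ρσ² to the variance of the sum. So Var(mean) = (σ²/N)(1 + 2mρ/N). Resampling by enrollment estimates only σ²/N. Hence:
- width ratio f = √(1 + 2mρ/N)
- actual coverage of the nominal 95% interval = 2Φ(1.96/f) − 1

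For m = 20 and ρ = 0.5: 1 + 2×20×0.5/70 = 1.286, so f = 1.134 and coverage is 91.6%.

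| People with two records | f, ρ = 0.3 | Coverage | f, ρ = 0.5 | Coverage |
|---|---|---|---|---|
| 5 | 1.02 | 94.5% | 1.03 | 94.2% |
| 10 | 1.04 | 94.0% | 1.07 | 93.3% |
| 20 | 1.08 | 93.0% | 1.13 | 91.6% |
| 25 | 1.10 | 92.5% | 1.17 | 90.8% |

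With m = 0 or ρ = 0, f is exactly 1. With ρ = −0.2 and m = 20, f is 0.94 and the SAP interval is slightly too wide.

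**Simulation of the bootstrap itself.** The settings were N = 70, 1,000 balanced replicates, percentile limits (assumed) and 1,500 trials; Monte Carlo error is about 0.6 points.

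| m | ρ | Coverage, by enrollment | Coverage, by person | Width ratio |
|---|---|---|---|---|
| 0 | – | 93.7% | 94.1% | 1.00 |
| 5 | 0.5 | 94.1% | 95.0% | 1.03 |
| 10 | 0.5 | 92.1% | 93.5% | 1.06 |
| 20 | 0.3 | 92.9% | 94.8% | 1.07 |
| 20 | 0.5 | 90.5% | 94.1% | 1.13 |

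The width ratios agree with the formula, and resampling by person restores coverage to about 94–95%. Coverage is a little under 95% even with no repeats, so not all of the shortfall comes from clustering. The formula is therefore the better guide to the size.

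**Where it applies.** All cohorts share Weeks 2 and 4. In the main treatment period, Weeks 8 and 12 contain only Cohorts 1–3, and SAP 4 puts the extension in a separate plan. Re-entry from a QD to a BID cohort therefore cannot affect the Week 8 or Week 12 intervals. Within any one cohort, a person who re-enrolls elsewhere appears once.

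**The case against.** The strongest reply concerns size. The documents give neither the repeat count nor the correlation, and several provisions could keep repeats few. The extension offers up to two years of treatment without re-enrolling (Protocol 3.1.3), re-entry needs a washout, and Cohorts 4–9 have an A4 entry range (inclusion criterion 4). Participants who come from another tildacerfont study add only one record here. The correlation may also be modest. The variable is change from a fresh baseline, which removes stable differences in level; regimens differ between QD and BID cohorts; and GC doses may be adjusted in Cohorts 1–3. The analysis is exploratory, and SAP 10.5 asks for caution in interpretation. All of this stands, and it is why the effect is given as a range. None of it alters the written sampling rule.

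A reader might also infer that the overall responder intervals, the "95% Exact (Clopper-Pearson) CIs and reported for the study and each cohort" of SAP 13.1.1.1.1, are too narrow for the same reason. The documents do not establish that. SAP 13.1.1 divides by the number of subjects in the PD analysis set. SAP 9.2.2 prescribes counting by enrollment for disposition, deviations and drug exposure; for efficacy it mentions only multiple baselines. Whether a person can count twice is left open. Exact intervals are also conservative. Simulated with 70 records, true proportions of 0.5 to 0.9 and a correlation of 0.3 to 0.5, they still cover about 94–96% with 5 or 10 repeats. At 25 repeats coverage falls to about 91–94%.

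Two further inferences are not supported. Table layouts sit in separate mock-shells (SAP 9), so it cannot be said that the number of distinct people will go unreported. The text of SAP 9.2.1, on re-enrollment into the same cohort, was not available to check, so nothing is claimed about that case.

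**Conclusion.** The point holds for the overall bootstrap intervals in SAP 13.2.1. The resampling unit is stated outright, repeat enrollment is planned for, and nothing in the text consulted offsets it. The intervals are too narrow provided that at least one person contributes more than one record to the pooled set and that the within-person correlation is positive. Positive correlation is a reasonable expectation but is not documented.

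At 70 records and a correlation of 0.3 to 0.5, the understatement is small with 5–10 repeats and moderate with 20. With 25 repeats the correct interval would be about 10–17% wider, and the SAP interval would cover about 91–92.5%. That case should not be read as the expected one. The consequence is overstated precision in a descriptive analysis. For the overall responder proportions the finding is only that the counting rule is unclear.

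**What to change.** In SAP 13.2.1, for the overall estimate, make the person the sampling unit. Link enrollments with a person-level ID, draw people with replacement, and carry all of a drawn person's enrollments into the replicate. The balanced scheme, 1,000 replicates and seed can stay. The point estimate over enrollments does not change. Show the number of distinct people beside the number of enrollments wherever results are pooled.

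In SAP 13.1.1 and 13.2.3, state whether the overall responder proportion counts people or enrollments. If it counts enrollments, there are two options:
- keep the exact interval, computed on one prespecified enrollment per person; this drops later records and can change the pooled estimate
- use a person-clustered interval that does not collapse to zero width at 0% or 100%, as a plain bootstrap would

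The cost is a linking ID, a short SAP edit before database lock, and slightly wider overall intervals. If repeats turn out to be few, the results barely change.

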### *13.2.2 Change from Baseline in PD Biomarker Ratios*

The change from baseline in select PD ratios will also be summarized and listed:

- A4/T (males only)

### *13.2.3 Proportion of Subjects with Reduction in PD Biomarkers*

The frequency and proportion (expressed as percentages) and the Exact 95% CI of subjects with a reduction (any reduction;  $\geq 50\%$  reduction; normalization [ $\leq$  ULN]) in PD biomarkers at Weeks 4 through Week 12 will be summarized descriptively overall, by cohort, and by subgroup ([Section 10.7](#)).

### *13.2.4 Change from Baseline in Glucocorticoid Total Daily Dose*

The following metrics of GC reduction include change from baseline (mg in HCe), change adjusted for BSA (mg/m^2), and percent change from baseline. These measurements of change from baseline in GC total daily dose at Week 12 will be summarized by cohort and overall. A listing of GC reduction will be provided.

The proportion of subjects who achieve the following criteria will be summarized in a table with descriptive statistics by cohort and scheduled time point:

- Any GC reduction
- $\geq 1 \text{ mg/m}^2$  GC reduction or any reduction from baseline in A4 at Week 12 (secondary efficacy endpoint).

A listing of prior and concomitant GC medications will provide information about subjects whose baseline dosing  $> 3 \times$  daily decreases frequency of administration  $\leq 3 \times$  daily.

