8.3.6. Pharmacodynamic Analyses

The PD Population will be used for all PD analyses.

Change from baseline in PD biomarkers, ACTH, 17-OHP, A4, testosterone, and 11KT will be summarized descriptively using the 8-point summary as well as geometric mean ratios comparing baseline to post baseline, as appropriate. T will be summarized separately for males and females.

Change from baseline in select PD ratios will also be summarized, A4/T (males only) and 11KT/T (males and females, separately). Other ratios may be identified in the statistical analysis plan.

The proportion of participants with a reduction in biomarkers at Weeks 4 (all cohorts) and 12 (Cohorts 1 to 3 only) will be summarized descriptively, including by subgroup, baseline A4 \leq ULN, Baseline A4 $>$ ULN:

- Any reduction
- \geq 50% reduction
- A4 \leq ULN

Change from baseline in GC total daily dose at Week 12 and during the extension period will be summarized descriptively:

- Absolute change (mg)
- Absolute change adjusted for body surface area (mg/m²)
- Percent change (%)
- Proportion of participants with GC reduction
- Proportion of participants with baseline dosing $>$ 3x daily who decrease frequency of administration \leq 3x daily

The proportion of participant with a \geq 1 mg/m² GC reduction or any reduction from baseline in A4 at Week 12 will be summarized descriptively.

Changes in adrenal biomarkers and GC will be summarized in a similar manner for the extension period.

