**Table 3 Objectives and Endpoints**

Cohorts 1-3 (12-week Treatment)			
	Objective	Endpoint	Section Number
1.	Primary		
1.1.	To evaluate the safety of tildacerfont in pediatric subjects with CAH	AEs and SAEs	14.1
2.	Secondary		
2.1.	To determine the efficacy of tildacerfont on disease control or reduction of GC use in subjects with classic CAH during 12 weeks of treatment	Proportion of subjects who achieve a reduction in A4 or reduction in GC dosing during treatment period	13.1.1
2.2.	To determine the efficacy of tildacerfont on disease control in subjects with classic CAH after 4 or 12 weeks of treatment	
 
• Proportion of subjects with elevated baseline A4 who achieve a reduction in A4 at Week 4
 
• Proportion of subjects with elevated baseline A4 who achieve A4 normalization at Week 4 or Week 12
 
	13.1.2
2.3.	To determine the consistency of preliminary tildacerfont PK in subjects with those simulated in a PBPK model	Tildacerfont plasma concentrations will be compared with the current PBPK simulation for consistency	Provided in a separate SAP
3.	Exploratory		
3.1.	To explore changes in PD biomarkers in pediatric subjects with CAH	Change from baseline in adrenocorticotrophic hormone (ACTH), 17hydroxyprogesterone (17-OHP), A4, and testosterone	13.2.1
COHORTS 4, 5, 6, 8, 7, and 9 (4-week Treatment)			
4.	Primary		
4.1	To evaluate the safety of tildacerfont in subjects with CAH	Adverse events (AEs) and serious adverse events (SAEs)	14.1
5.	Secondary		
5.1	To determine the efficacy of tildacerfont on disease control in subjects with classic CAH after 4 weeks of treatment	
 
• Proportion of subjects who achieve reduction in androstenedione (A4) at Week 4
 
• Proportion of patients who achieve A4 normalization at Week 4.
 
	13.1.1
5.2	To determine the consistency of preliminary tildacerfont pharmacokinetics (PK) in subjects with those simulated in a physiologically based PK (PBPK) model	Tildacerfont plasma concentrations will be compared with the current PBPK simulation for consistency	Provided in a separate SAP
6.	Exploratory		
6.1	To explore changes in pharmacodynamic (PD) biomarkers in subjects with CAH	Change from baseline in adrenocorticotrophic hormone (ACTH), 17hydroxyprogesterone (17-OHP), A4, testosterone	13.2.1

EXTENSION (Cohorts 1-9)			
7.	Primary		

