### 9.4.7 *Body Surface Area*

Body surface area is calculated per the Mosteller formula as  $\text{sqrt}((\text{height} (\text{cm}) \times \text{weight} (\text{kg})) / 3600)$ , rounded to one decimal place. The most recent height measured will be used in all BSA calculations.

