#### 9.4.14 Responder Definitions

The second secondary efficacy and exploratory variables are proportions of responders based on serum PD assessments and GC dosing. Indicator variables for each responder criteria are defined in [Table 5](#).

**Table 5** Responder Definition by Endpoint

Endpoint	Definition	
Composite: Proportion of subjects who achieve reduction in A4 OR reduction in GC dosing (Cohorts 1 through 3) at a postbaseline visit	1	Reduction in A4 OR reduction in GC Dose
	0	(no reduction in A4 AND no reduction in GC Dose) OR missing
Proportion of subjects with elevated baseline A4 who achieve a reduction in A4 at a post-baseline visit	1	Baseline A4 > ULN AND reduction in A4
	0	Baseline A4 ≤ ULN OR no reduction in A4 OR missing
Any reduction at a postbaseline visit	1	Reduction from baseline
	0	No reduction from baseline OR missing
≥ 50% reduction at a postbaseline visit	1	≥ 50% reduction from baseline
	0	< 50% reduction from baseline OR missing
≤ ULN at a post-baseline visit	1	≤ ULN
	0	> ULN OR missing

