### 13.1 Secondary Efficacy Analysis

The secondary “treatment policy” estimands are evaluated by two secondary efficacy assessments.

#### 13.1.1 Reduction in A4 or Reduction in GC Dosing at Week 12

Population: The analysis population for the secondary efficacy analyses is the PD analysis set.

Variable: The analysis variable is the proportion of subjects in the PD analysis set who are responders (defined in [Table 5](#)). This proportion is calculated for each cohort as the number of subjects at Week 12 (at Week 4 for cohorts 4 through 9) who have a reduction of A4 or reduction in GC reduction, divided by the total number of subjects in the PD analysis who were enrolled in each cohort. This proportion is also calculated to evaluate the overall subjects at Week 12 (at Week 4 for cohorts 4 through 9) by pooling the responders and dividing by the total number of subjects in the PD analysis set.

Subjects with missing A4 or GC dosing information at a given visit are assumed to be non-responders at that visit. Subjects who do not have a reduction from baseline in A4 or a reduction in GC dose are considered non-responders.

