## 15 CHANGES RELATIVE TO THE PROTOCOL-SPECIFIED ANALYSIS

Study Protocol Section 8.2 defines the PD population as including “all subjects in the Safety Population with at least 1 evaluable post-baseline PD assessment.” Given the vague language in the protocol of how to determine eligibility for the PD population – if for example a subject must have a non-missing post-baseline from all six hormones (ACTH, 17-OHP, A4, testosterone, and 11KT), of any of the six PD hormones, or one specific hormone, the SAP added the specificity that the PD population includes “all subjects in the Safety Analysis Set with a baseline A4 assessment and at least one evaluable post-baseline PD A4 assessment” to align with the A4-dependent secondary efficacy analyses.

SAP [Section 8](#) additionally defines the Elevated Baseline Pharmacodynamic Analysis Set to support the secondary efficacy analysis of subjects with elevated baseline A4 who achieve a reduction in A4 at Week 4.

The Study Protocol Section 8.3.6 specifies that the hormone, 11-ketotestosterone (11-KT), will be summarized as part of the pharmacodynamic analyses, including: general summary statistics by visit, 11-KT/T ratio summaries by visit for males and females; and proportion of subjects with any reduction in 11-KT, a  $\geq 50\%$  reduction in 11-KT, and a normalization of 11-KT ( $11\text{-KT} \leq \text{ULN}$ ). 11-KT assessments, however, will not be provided to Spruce for this study. There are no standard assay or normal references of 11-KT for children. In addition, developing and validating an assay could not be completed in time for this study. Therefore, any protocol specified pharmacodynamic and exploratory endpoints for 11-KT will not be performed.

The Study Protocol Section 8.3.6 mentions that exploratory endpoint of the proportion of subjects with baseline dosing  $> 3 \times$  daily who decrease frequency of administration  $\leq 3 \times$  daily. Given that the dose frequency is collected in a free text form in the Concomitant Medication eCRF form, the dose frequencies are not standardized and easily analyzable, therefore GC medications will only be listed and not summarized to provide information supporting this exploratory endpoint.

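### SAP 13.2.4 puts a ≥1 mg/m² GC threshold on the Week 12 composite secondary endpoint, which SAP Table 5 and 13.1.1 score with no threshold; separately, BSA is rounded before it is used as a divisor

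*SAP*

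**What the plan says.** **The rule with no threshold.** SAP Table 3 words the first secondary endpoint for Cohorts 1-3 as "Proportion of subjects who achieve a reduction in A4 or reduction in GC dosing during treatment period" and sends the reader to 13.1.1. In SAP Table 5 (Section 9.4.14) a participant scores 0 on the composite when there is "no reduction in A4 AND no reduction in GC Dose", or when data are missing. Section 13.1.1 agrees: "Subjects who do not have a reduction from baseline in A4 or a reduction in GC dose are considered non-responders". None of these gives a minimum GC reduction or a unit. The endpoint table in Protocol Section 2 has no threshold either.

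**The rule with a threshold.** SAP 13.2.4 lists two criteria: any GC reduction, and a second one that opens with ≥1 mg/m² and continues "GC reduction or any reduction from baseline in A4 at Week 12 (secondary efficacy endpoint". The same criterion stands in Protocol 8.3.6, "GC reduction or any reduction from baseline in A4 at Week 12 will be summarized descriptively", where it is not called the secondary endpoint.

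**Reconciliation.** SAP Section 15 discusses other parts of Protocol 8.3.6, namely 11-KT and dosing frequency ("The Study Protocol Section 8.3.6 mentions that exploratory endpoint of the proportion of subjects with baseline dosing" and so on). It does not mention the threshold.

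**BSA.** SAP 9.4.7 gives the Mosteller formula and then says "rounded to one decimal place. The most recent height measured will be used in all BSA calculations". Section 9.4.17.2 divides the GC dose by that BSA.

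**The concern.** This is the first-listed secondary efficacy endpoint for Cohorts 1-3. A programmer working from Table 5 and 13.1.1 and another working from 13.2.4 could report different rates, and each could point to SAP text that calls the result secondary. The study is open-label, so which rule is used could come to depend on the data. SAP Section 4 makes the SAP govern where it differs from the protocol, but that does not help when the conflict is inside the SAP.

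The rounding matters for a different reason. In small children 0.1 m² is a large fraction of BSA. Rounding the divisor can create or hide a change of the size that the threshold is meant to detect.

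**Working it through.** The documents give no responder rate or power figure to reproduce. The check compares the rules and then works through examples. Heights, weights and doses below are illustrative assumptions.

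**1. Where the two rules differ**

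- Mosteller BSA = √(height in cm × weight in kg / 3600).
- At 140 cm and 34 kg: √(140 × 34 / 3600) = √1.3222 = 1.150 m².
- GC from 14 to 13 mg/day with BSA unchanged: 1 / 1.150 = 0.87 mg/m². With the rounded BSA of 1.1 m² it is 1 / 1.1 = 0.91 mg/m².
- If A4 is not lower, this is a responder under Table 5 and 13.1.1 and a non-responder under 13.2.4.

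At a fixed BSA the rules differ only for net cuts below 1 mg/m². As a share of the starting dose that is below 1/9 = 11.1% at an assumed 9 mg/m²/day and below 1/14 = 7.1% at an assumed 14 mg/m²/day. Protocol 5.3.1.2 gives the direction of GC changes and refers to the Pharmacy Manual for further guidance. Step sizes are in neither document, so the frequency of such cuts cannot be derived.

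**2. Effect of one participant**, with the exact Clopper-Pearson 95% intervals of SAP 13.1.1.1.1 and planned cohort sizes of 5 and 10:

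- n = 5: 1/5 = 20 points. For example, 3/5 = 60% (14.7 to 94.7) becomes 2/5 = 40% (5.3 to 85.3).
- n = 10: 1/10 = 10 points. For example, 6/10 = 60% (26.2 to 87.8) becomes 5/10 = 50% (18.7 to 81.3).

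**3. Rounding BSA before division**

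Take 115 cm, an unchanged 12 mg/day, and weight going from 22.5 to 23.0 kg:

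- Unrounded BSA: √(115 × 22.5 / 3600) = 0.848 and √(115 × 23.0 / 3600) = 0.857 m². Dose: 12 / 0.848 = 14.15 and 12 / 0.857 = 14.00 mg/m². Fall: 0.15 mg/m².
- Rounded BSA: 0.8 and 0.9 m². Dose: 12 / 0.8 = 15.00 and 12 / 0.9 = 13.33 mg/m². Fall: 1.67 mg/m².

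With rounding, a half-kilogram gain on an unchanged dose meets the ≥1 mg/m² criterion.

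This depends on using the BSA of each visit. SAP 9.4.17.2 defines only the baseline BSA-based dose. Visit-specific BSA is inferred from 5.3.1.4 (BSA from the most recent measurements) and 12.3 (BSA-adjusted dose by time point). If the change is instead the mg difference divided by a BSA, an unchanged dose gives 0 / BSA = 0 whether or not BSA is rounded. A rule in mg is not affected at all.

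**4. The first example under visit-specific BSA**

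If the 34 kg child reaches 34.5 kg, BSA goes from 1.150 to 1.158 m², which rounds from 1.1 to 1.2. The fall is 14/1.1 − 13/1.2 = 12.73 − 10.83 = 1.89 mg/m², and the child responds under both rules. Unrounded, a gain to 35 kg (BSA 1.167) gives 14/1.150 − 13/1.167 = 1.03 mg/m². The 0.87 figure therefore holds only with BSA held fixed.

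**The case against.** The best reply is that the conflict comes down to one misplaced label. Table 3 maps the endpoint to 13.1.1, and Table 3, Table 5, 13.1.1 and Protocol Section 2 all agree. Section 13.2.4 sits under exploratory analyses and carries over a summary that Protocol 8.3.6 never called secondary. No protocol analysis has been dropped, so Section 15 hides no departure. Most of this stands, and it is why the simplest repair follows the majority text. But the label is in the SAP, beside a separate bullet for any GC reduction, so the document itself treats the two criteria as distinct and calls the stricter one secondary.

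The rounding point also has limits. It depends on an inferred use of visit-specific BSA, touches only mg/m² values, and can work in either direction, because rounding can also hide a real cut near 1 mg/m².

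A reader might go further and infer three things that the documents do not support:

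- *That an inert drug would yield some particular high response rate.* Any such figure needs the share with A4 within normal limits, adherence to the algorithm, GC step sizes and A4 variability. The documents do not give these for this population.
- *That the unqualified rule always gives the higher rate.* With visit-specific BSA the rules are not nested: an unchanged mg dose can meet ≥1 mg/m².
- *That the lack of a table crossing A4 direction with GC direction is an error.* SAP 13.1 declares a treatment-policy estimand, A4 and GC are summarised separately, GC data are listed by subject, and the table shells are in a separate document.

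**Conclusion.** The contradiction is real and needs no assumption: one labelled secondary endpoint has two scoring rules inside the SAP, and nothing in the SAP chooses between them. A single affected participant moves a cohort's rate by 20 points at n = 5 or 10 points at n = 10. The number affected is unknown and could be zero if GC steps are large. The endpoint is descriptive and uncontrolled and the primary objective is safety, so no type I error or power is involved. What is lost is a single pre-specified result.

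Rounding BSA before division is a smaller error. It is conditional on visit-specific BSA and confined to mg/m² values. Its net effect on the composite rate cannot be determined from the documents, in size or in sign, so it should not be described as inflating the rate.

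**What to change.** - **One definition.** State the secondary composite once, with its unit, and use it in Table 5, 13.1.1 and 13.2.4. The simplest choice keeps the unqualified rule of Table 3, Table 5, 13.1.1 and Protocol Section 2, specified as any reduction in total daily GC dose in mg hydrocortisone equivalents. Delete the parenthetical label from 13.2.4 and report the ≥1 mg/m² version as supportive. If the sponsor intended the threshold, carry it into Table 5 and 13.1.1 and make any reduction the supportive summary. Record the choice in Section 15.
- **BSA.** Remove the rounding instruction from 9.4.7, calculate with unrounded BSA, and round only for display.
- **Optional.** Tabulate Week 12 responders by A4 direction and GC direction as a descriptive aid, accepting small cells.

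The cost is SAP wording and minor programming, plus one table if the optional item is taken up; no new data are needed. Protocol 1.2.3 shows that open-label data from Cohorts 1-3 already exist, so the Section 15 entry should say that the clarification came after them.
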